7.1 Screening Visits

7.1.1 Visit 00A, Day -4 to -1, Screening 1, icddr,b or Rajshahi Medical College Hospitals

Potential adult subjects from Bangladesh (between the ages of 18-65) will be chosen from adult patients presenting to the icddr,b or Rajshahi Medical College Hospitals with mild diarrhea. These potential subjects will be visited by a study team member or health professional from icddr,b or Rajshahi Medical College Hospitals. Screening may take place as many as 4 days prior to enrollment. A 5-minute screener will be administered at the first screening visit and will be used to identify eligible persons who will be referred to a study team member to discuss inclusion in the study. Written informed consent will be obtained from potentially eligible subjects after the 5-minute screener and prior to conducting any further screening or study procedures. A single ICF will be used to document the volunteer's consent to further screening and participation in the study.

For subjects who are potentially eligible and who have provided informed consent, the following procedures will be conducted at the first screening visit:

- Full eligibility criteria will be reviewed with subjects.
- Demographic data, including date of birth, sex, self-reported ethnicity, and residence location will be collected.
- A stool sample will be collected for detection of *Giardia* or *E. histolytica*.

7.1.2 Visit 00B, Day -4 to -1, Screening 2, icddr, b or Rajshahi Medical College Hospitals

Only eligible subjects who have provided informed consent and stool specimens that are positive for *Giardia* or *E. histolytica* will have this second screening visit for blood and urine testing. This visit may also occur on the same day at Visit 00A and must occur at the hospital or clinic.

- Medical history will be obtained by interview of subjects to assure eligibility.
- All concomitant medications taken within 30 days prior to signing the informed consent form will be recorded on the appropriate data collection form and eCRF. Subjects will be questioned specifically about any metronidazole in the past 7 days.
- A targeted physical examination will be performed, including vital signs (oral temperature, pulse (taken at the wrist or neck), blood pressure) observation for rashes or glossitis, and an abdominal exam.
- A urine pregnancy test will be performed on all female subjects of childbearing potential and must be negative.

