- Approximately 17 mL of venous blood will be collected for CBC, ALT, AST, BUN, and creatinine tests. These values must be confirmed to meet the eligibility criteria as outlined in the Subject Inclusion Criteria (see Section 5.1) prior to randomization.
- A urine sample will be collected to test for the presence of protein. The result must be confirmed to meet the eligibility criteria as outlined in the Subject Inclusion Criteria (see Section 5.1) prior to randomization.

7.2 Visit 01, Day 1, Enrollment, Dose 1, icddr,b or Rajshahi Medical College Hospital or Clinic

- Enrollment and randomization of subjects
- Eligibility criteria, including results of all clinical screening laboratory evaluations, will be reviewed with subjects to assure continued eligibility.
- Targeted physical exam performed, if indicated
- 2 capsules of study product (6mg total) or placebo will be orally taken by the subject.
- Assessment of any new symptoms since Visit 00B before first dose is given.
- Medical history, including any concomitant medications, reviewed.
- Stool sample will be collected for ova and parasite testing. The window for stool specimens will be +1 day and the date of collection noted.

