7.3 Follow-up Visits

This section summarizes the follow-up procedures conducted for each subject. Complete details for each Study Day are provided in Appendix A. Visit windows are specified around the target for each visit. Follow-up visits are scheduled in reference to dosing dates as indicated for each visit window. Subjects will be enrolled at the icddr,b or Rajshahi Medical College Hospitals and have follow-up visits in the Hospital until their diarrhea has resolved. Subsequent follow-up visits may be held at the icddr,b, Rajshahi Hospital, or clinic or their home except for Visit 07 which must be at icddr,b or Rajshahi Hospital or clinic because blood drawing is required. When a visit falls on a holiday Friday, two days' supply of study product will be given on Thursday and the Friday dose will be self-administered as instructed and documented upon the next visit. Staff will notify the subject on Friday to take the dose and document it was taken. The window for stool specimens will be +1 day and the date of collection noted. For visits that fall on a Friday, the study team member will confirm on the next scheduled visit the diarrhea status as noted on the Visit Documentation for the **missed** visit. This will be submitted in the Data System for study end-point analysis.

7.3.1 Visit 02, Day 2

- Targeted physical exam performed, if indicated.
- 2 capsules of study product (6mg total) or placebo will be orally taken by the subject.
- Assessment of any side effects or adverse events.
- Any subject with worsening diarrhea as assessed by the study physician, may have their dose discontinued and receive standard of care metronidazole.
- Medical history, including any concomitant medications, reviewed.

7.3.2 Visit 03, Day 3

- Targeted physical exam performed, if indicated.
- 2 capsules of study product (6mg total) or placebo will be orally taken by the subject.
- Assessment of any side effects or adverse events.
- Any subject with worsening diarrhea as assessed by the study physician, may have their dose discontinued and receive standard of care metronidazole.

- Medical history, including any concomitant medications, reviewed.
- Stool sample will be collected for ova and parasite testing. The window for stool specimens will be +1 day and the date of collection noted.

7.3.3 Visit 04, Day 4

- Targeted physical exam performed, if indicated.
- 2 capsules of study product (6mg total) will be orally taken by the subject.

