8 STUDY PROCEDURES/EVALUATIONS

8.1 Clinical Evaluations

Medical History: Complete medical history will be obtained by interview of the subjects at the screening visit (Visit 00B) and will be reviewed and updated on Day 1 (Visit 01) prior to the first study product administration. Subjects will be queried regarding a history of significant medical disorders of the head, eyes, ears, nose, throat, mouth, cardiovascular system, lungs, gastrointestinal tract, liver, pancreas, kidney, urologic system, nervous system, blood, lymph nodes, endocrine system, musculoskeletal system, skin, and genital/reproductive tract. A history of any allergies, cancer, immunodeficiency, psychiatric illness, substance abuse, and autoimmune disease will be solicited. At follow-up visits after the first dose, an interim medical history will be obtained, when indicated, by interview of the subjects noting any changes since the previous visit.

Concomitant Medications: Concomitant medications will include a review of all current medications and medications taken within 30 days prior to signing the informed consent form and through approximately 30 days after the first study product administration. Prescription and over-the-counter drugs will be included as well as vitamins and supplements. Assessment of eligibility will also include a review of all permitted and prohibited medications per the Subject Inclusion and Exclusion Criteria (see Section 5).

Physical Examination and Vital Signs: A physical examination limited to vital signs (blood pressure, pulse, temperature), observation for rashes or glossitis, and an abdominal exam will be performed at screening (Visit 00B). On Day 1 (Visit 01) prior to the first study product administration and at follow-up visits after the first administration of study product, a targeted physical examination will be performed, if indicated, based on subject's interim medical history.

Adverse Events: Subjects will be interviewed to determine the occurrence of unsolicited AEs.

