9.2 Methods and Timing for Assessing, Recording, and Analyzing Safety Parameters

9.2.1 Adverse Events

Adverse Event: International Conference on Harmonisation (ICH) E6 defines an AE as any untoward medical occurrence in a patient or clinical investigation subject administered a pharmaceutical product regardless of its causal relationship to the study treatment. An AE can therefore be any unfavorable and unintended sign (including an abnormal laboratory finding), symptom, or disease temporally associated with the use of a medicinal (investigational) product. The occurrence of an AE may come to the attention of study personnel during study visits and interviews of a study recipient presenting for medical care, or upon review by a study monitor.

AEs not meeting the protocol-defined criteria for SAEs will be captured on the appropriate data collection form and electronic case report form (eCRF). Information to be collected for unsolicited AEs includes event description, date of onset, licensed clinician's assessment of severity and relationship to study product and alternate etiology (if not related to study product) (assessed only by those with the training and authority to make a diagnosis and listed on the Form FDA 1572 as the site principal investigator or sub-investigator), date of resolution of the event, seriousness and outcome. AEs while on study will be documented appropriately regardless of relationship. AEs will be followed to resolution.

Any medical condition that is present at the time that the subject is screened will be considered as baseline and not reported as an AE. However, if the severity of any pre-existing medical condition increases, it will be recorded as an AE.

AEs must be graded for severity and assessed for relationship to study product (see definitions below). Adverse events characterized as intermittent require documentation of onset and duration of each episode. The start and stop date of each reported AE will be recorded on the appropriate data collection form and eCRF.

FDA defines an AE as any untoward medical occurrence associated with the use of a drug in humans, whether or not considered drug related.

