9.2.2 Solicited Events

Solicited events are AEs that are known to occur with this study product. Solicited AEs will not be collected that are related to any prescribed metronidazole. The below Toxicity Grading Scales will be used to grade events.

Adverse event data will be collected at each visit using specific questions and/or targeted physical examination. Based on the adverse reactions listed on the package insert, expected side effects include: loose stools or diarrhea, abdominal pain, nausea with or without vomiting, constipation, anorexia, flatulence, dyspepsia, dysgeusia, pruritus, hair loss, urticarial, stomatitis, conjunctivitis,

glossitis, and hematuria. Diarrhea, however, will not be recorded as a side effect because all participants will enroll with diarrhea, and because its resolution is the endpoint of the study. Physical examinations will look for abdominal pain, hair loss, urticaria, rashes, stomatitis, conjunctivitis, and glossitis. Hematologic, renal, or hepatic laboratory abnormalities will be picked up on testing at Day 7. Adverse event collection will continue until Day 28 (following three half-lives of the drug).

Event	Mild (Grade 1)	Moderate (Grade 2)	Severe (Grade 3)
Loose stools or diarrhea	Does not interfere with daily activity	Interferes with daily activity	Prevents daily activity (incapacitating)
Abdominal Pain	Does not interfere with daily activity	Interferes with daily activity	Prevents daily activity (incapacitating)
Nausea with or without vomiting	Does not interfere with daily activity	Interferes with daily activity	Prevents daily activity (incapacitating)
Constipation	Does not interfere with daily activity	Interferes with daily activity	Prevents daily activity (incapacitating)
Anorexia	Does not interfere with daily activity	Interferes with daily activity	Prevents daily activity (incapacitating)
Flatulence	Does not interfere with daily activity	Interferes with daily activity	Prevents daily activity (incapacitating)
Dyspepsia	Does not interfere with daily activity	Interferes with daily activity	Prevents daily activity (incapacitating)
Dysgeusia	Does not interfere with daily activity	Interferes with daily activity	Prevents daily activity (incapacitating)
Pruritus	Does not interfere with daily activity	Interferes with daily activity	Prevents daily activity (incapacitating)
Hair loss	Does not interfere with daily activity	Interferes with daily activity	Prevents daily activity (incapacitating)

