APPENDIX A: SCHEDULE OF EVENTS

Procedure	Visit* Number	00A	00B	01	02	03	04	05	06 ²	07	08	09	10 ²
	Study Day	-4	-4	1	2	3	4	5	6	7	14	28	30
	Window (days)	-4 to1	-4 to -1	+1 ⁶ ---	---	--+1-	---	+1 ⁶ ---	---	+1	+/-3	+/-3	+/-3
Review Eligibility		X		X									
Informed Consent		X											
Demographic Data		X											
Medical History			X	X	X	X	X	X	X	X	X	X	
Targeted Physical Exam ³			X	X	X	X	X	X	X	X	X	X	
Vital signs ⁴			X	X									
Concomitant Medications			X	X	X	X	X	X	X	X	X	X	
Randomization/ Enrollment				X									
Assessment for side effects of treatment					X	X	X	X	X	X	X	X	
AEs/SAEs				X	X	X	X	X	X	X	X	X	
Urine for pregnancy testing			X										
Treatment (giardiasis subjects)				X	X	X	X	X					

Treatment (E. histolytica)				X	X	X	X	X	X	X			
Procedure	Visit Number	00A	00B	01	02	03	04	05	06 ³	07	08	09	10 ⁴
	Study Day	-4	-3	1	2	3	4	5	6	7	14	28	30
	Window (days)	-4 to 1	-3 to -1	+1 ⁸ ---	---	--+1 ⁸ -	---	+1 ⁸ ---	---	+1	+/-3	+/-3	+/-3
Urine Dipstick for Proteinuria			X							X			
Complete Blood Count ⁵			X							X			
BUN			X							X			
Creatinine			X							X			
ALT			X							X			
AST			X							X			
Stool specimen ⁶		X		X		X		X		X	X	X	
Blood volume			17							17			
Blood volume totals			17							34			
Standard of Care Treatment													X

*Subjects will be enrolled at the icddr,b or Rajshahi Hospitals and have follow-up visits until their diarrhea has resolved. Subsequent follow-up visits may be held at the icddr,b or Rajshahi Hospital, or local (to Rajshahi) clinic or their home except for Visit 07 which must be performed at icddr,b or Rajshahi Hospital or Clinic because blood drawing is required.

¹Visit 06 will only be conducted for subjects receiving treatment for amebiasis.

²Visit 10 will only be conducted for subjects who remain positive for amebiasis or giardiasis at Day 28 and have not previously received standard of care treatment.

³Targeted physical exam may also include observations for rashes, hair loss, urticaria or glossitis, and an abdominal exam.

⁴Vital signs (oral temperature, pulse, blood pressure)

⁵Complete blood count includes white blood cells, hemoglobin, and platelet count.

⁶Window of + 1 day for stool specimens after (and including) Day 1. Date of collection will be noted. The window does not apply to treatment administration or other required assessments.

⁷Amebiasis patients only

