9.3. Adverse Events

9.3.1. Solicited Events and Symptoms

Adverse event data is collected at each visit using specific questions and/or targeted physical examination. Based on the adverse reactions that have been observed with the use of auranofin in previous studies, the following solicited events are tracked: loose stools or diarrhea, abdominal pain, nausea with or without vomiting, constipation, anorexia, flatulence, dyspepsia, dysgeusia, pruritus, hair loss, urticaria, stomatitis, conjunctivitis, glossitis, hematuria, and rash. Hematologic, renal, or hepatic laboratory abnormalities are

picked up on testing at day 7. Adverse event collection continues until Day 28 (following three half-lives of the drug). As the drug is administered orally, no local event reactivity is recorded.

Table 35 and **Table 36** display the number, percentage, and 95% confidence interval for the percentage of subjects experiencing each solicited adverse event, by treatment group, separately for the amebiasis group and the giardiasis group. Solicited adverse events are also displayed graphically. **Figure 5** displays the maximum severity of solicited symptoms per subject by day post treatment, for each treatment group and for both treatment groups combined, separately for each disease group and study population.

Solicited systemic events by subject will be presented in [Listing 19](#), [Listing 20](#), [Listing 21](#), and [Listing 22](#).

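### The solicited symptom list is not graded before dose 1 and the solicited displays have no baseline rule, so the worsening rule in Protocol 9.2.1 cannot be applied reliably

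*Protocol*

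**What the plan says.** **When symptoms are asked about.** Protocol 9.2.2 gives the general rule: "Adverse event data will be collected at each visit using specific questions and/or targeted physical examination". In Appendix A the row "Assessment for side effects of treatment" is marked from Visit 02 to Visit 09 and not at Visits 00A, 00B or 01. The visit text agrees: "Assessment of any side effects or adverse events" first appears under Visit 02, Day 2 (Protocol 7.3.1). A separate AEs/SAEs row is marked from Visit 01, and Protocol 9.4 starts adverse event follow-up at first receipt of study drug.

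**What is done before dose 1.** At Visit 00B, "Medical history will be obtained by interview of subjects to assure eligibility" (Protocol 7.1.2). Section 8.1 asks for a complete history by body system, updated on Day 1 before dosing. The screening examination names rash, glossitis and the abdomen. At Visit 01 the plan requires "Assessment of any new symptoms since Visit 00B before first dose is given" (Protocol 7.2), and a targeted examination only if indicated.

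**How baseline is defined.** Section 9.2.1 treats a condition present at screening as baseline and not as an adverse event, and adds: "However, if the severity of any pre-existing medical condition increases, it will be recorded as an AE".

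**How the data are shown.** SAP 9.3.1 says Tables 35 and 36 "display the number, percentage, and 95% confidence interval for the percentage of subjects experiencing each solicited adverse event", by treatment group. Figure 5 shows maximum solicited severity by day after treatment and by arm. Both are repeated for the symptomatic groups. Diarrhea is left out as a side effect in those groups (Protocol 9.2.2; SAP Appendix 1).

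**The concern.** Several solicited symptoms, such as abdominal pain, nausea, anorexia and flatulence, can plausibly come from the intestinal infection itself, and every symptomatic subject enters with diarrhea. To say that a Day 2 complaint is new or worse, one needs to know whether it was there before dose 1 and how severe it was. The plan recognises this problem for diarrhea but makes no provision for the other symptoms on the list.

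At stake is the by-arm picture of solicited clinical toxicity in Tables 35-36 and Figure 5. Without a starting grade, staff may handle the same continuing pain differently: one leaves it out as baseline, another reports it because Protocol 9.2.1 says doubtful observations should be reported. Capsules can be told apart by their imprint (Protocol 5.3.2 and 6.1.2.2), so such discretion is best kept small.

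**Working it through.** **Step 1. Does the plan record what the worsening rule needs?**

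| Needed | What the plan provides before dose 1 |
|---|---|
| The same symptom list | A history by body system (00B) and a question limited to symptoms new since 00B (01). The list itself is not used |
| A severity grade for each symptom | None stated |
| The same signs | Section 9.2.2 later looks for seven: abdominal pain, hair loss, urticaria, rash, stomatitis, conjunctivitis, glossitis. Screening names rash, glossitis and the abdomen. An Appendix A footnote says the targeted examination may also cover hair loss and urticaria. Stomatitis and conjunctivitis are not named |
| A baseline date next to dosing | Baseline is screening, up to 4 days before dose 1. The status of symptoms that start in between is not defined |

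**Step 2. Do the displays supply the missing rule?** The shells of Tables 35-36 hold n, % and 95% CI per symptom, with no baseline row and no definition of new or worse. The text and title of Figure 5 mention no pre-dose severity. By contrast, the laboratory shells carry baseline rows (Tables 46-50) and change from baseline (Tables 59-66), and the vital-sign shells (Tables 67-78) have a baseline row.

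**Step 3. Illustration of size.** The plan states no figure on this point, so there is nothing to reproduce. Inputs:
- *d* = 14%, the abdominal pain rate for longer-term therapy in Protocol 9.1, taken as the drug-caused rate.
- *b* = share with abdominal pain at entry. The documents do not give it; assumed 0 to 60%.
- *c* = share of entry pain that auranofin relieves completely before it is first asked about; assumed 0 or 15%.
- 34 per arm within a disease group (Protocol 11.2).

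If every post-dose report is counted, placebo = *b* and auranofin = *b*(1 − *c*) + [1 − *b*(1 − *c*)]*d*. The difference is (1 − *b*)*d* − *bc*(1 − *d*).

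| *b* | Placebo | Auranofin (*c* = 0) | Difference (*c* = 0) | Background share of auranofin reports | Difference (*c* = 15%) |
|---|---|---|---|---|---|
| 0% | 0% | 14.0% | 14.0 points | 0% | 14.0 points |
| 20% | 20% | 31.2% | 11.2 | 64% | 8.6 |
| 40% | 40% | 48.4% | 8.4 | 83% | 3.2 |
| 60% | 60% | 65.6% | 5.6 | 91% | −2.1 |

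Example, *b* = 40%: 0.60 × 14 = 8.4; with relief, 8.4 − 0.40 × 0.15 × 86 = 8.4 − 5.16 = 3.2.

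**Step 4. The opposite reading.** Suppose staff dismiss every continuing symptom as baseline because no rise can be shown. Then only subjects free of pain at entry contribute, and the rates are (1 − *b*)*d* against 0. At *b* = 40% that is 8.4% against 0%. Both extremes lose *b* × *d* = 0.40 × 14 = 5.6 points of drug effect. This assumes that the drug would worsen existing pain at the same 14% rate.

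**Step 5. Precision.** No test is planned for these tables, so power is only a yardstick. Exact Fisher power at 34 per arm with *c* = 0 is 0.34, 0.12, 0.07 and 0.05 for *b* = 0, 20, 40 and 60%.

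**The case against.** Much can be said for the plan as written.

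- **Pre-dose questions exist.** A reader of Appendix A might infer that symptoms are first asked about after dosing. Protocol 7.1.2, 7.2 and 8.1 contradict that. What is missing is the list and the grade.
- **Section 9.2.1 is meant as a filter.** A reader might infer that the rules conflict, or that infection symptoms are simply counted as drug effects. The documents do not go so far. Solicited events are defined as adverse events, so 9.2.1 can be read as deciding what Tables 35-36 count. Relatedness is judged separately, and randomized placebo carries the same expected background at entry. What stands is that the filter cannot be applied evenly without a starting grade. Also, randomization balances entry symptoms but not their course if the drug works.
- **Tables 35-36 are not the only by-arm display.** Figure 5 is another, but it has the same gap.
- **Actual numbers may be small.** SAP Section 15 drops finer solicited tables because few events had been seen. It does not split by population, but it fits poorly with a high entry prevalence. Protocol 5 describes mild diarrhea in otherwise healthy adults.
- **The illustration leans one way.** The 14% comes from longer-term therapy. In Phase I, at 6 mg for 7 days, 1 of 15 subjects had treatment-related abdominal discomfort (Protocol 2.3.1). The relief column needs complete relief by Day 2 and none on placebo, which is demanding.
- **The remedy is partial.** With *d* = 14% and placebo new-or-worse rates of 10, 15 or 20%, Fisher power is 19, 15 or 12%. If auranofin also prevents 15% of that worsening, it is 15, 11 or 8%. So some offset from efficacy remains.

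These points limit the size of the problem. They do not supply the missing pre-dose grade.

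**Conclusion.** The point holds as a gap in measurement and derivation. Pre-dose symptom questions are unstructured and ungraded, the worsening rule in 9.2.1 therefore lacks its starting value for solicited symptoms, and the solicited displays state no baseline or treatment-emergent rule. Infection symptoms can enter as events, or a worsening can be set aside as baseline. Either dilutes or distorts the by-arm comparison.

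The size is unknown. Under the assumptions above, with no early relief, a 14-point effect would show as 11.2 to 5.6 points for entry prevalences of 20 to 60%. A reader might go on to infer that disease symptoms swamp the drug signal or make auranofin look falsely safe. The documents support neither, because they give no entry prevalence and no early relief rate. Diarrhea, the primary endpoints and the study halting rules in 9.4.1 (deaths, related SAEs, anaphylaxis) are not affected. The change is still worth making, because a pre-dose grade that was not taken cannot be recovered later.

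**What to change.** 1. **Protocol 7.2:** at Visit 01, before dose 1, ask and grade the same solicited list and look for the same signs as at later visits.
2. **Appendix A:** add an X at Visit 01 in the side-effect row, labelled pre-dose.
3. **Protocol 9.2.1:** define baseline for solicited events as the pre-dose Day 1 grade.
4. **SAP 9.3.1, symptomatic versions of Tables 35-36:** count an event when it is new or at least one grade above the pre-dose grade, and keep the all-report count as a second row. Show the pre-dose grade in Figure 5.
5. **Subjects already enrolled:** use the Visit 00B history and the Visit 01 symptom record as an ungraded baseline, and say so in a footnote.

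Cost: an existing form completed once more, a few minutes per subject, with no added visit or sample, plus a protocol amendment with its approvals and a form revision. Subjects already enrolled will still have no pre-dose grade. New-or-worse counting reduces the background but does not remove all offset from efficacy, and power for safety differences at 34 per arm stays low. The gain is an estimate that can be interpreted.
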